1.8. Assessment for Response

Response will be determined according to the IMWG response criteria for multiple myeloma (2006). Disease assessment for response will include Serum Protein Electrophoresis (SPEP), Urine Protein Electrophoresis (UPEP), Serum Free Light Chains (SFLC) and Immunoglobulins (Igs). Bone marrow procedures should be completed at the time of suspected near complete response (or very

good partial response when nCR cannot be determined). A serum sample from blood at landmark timepoints (after C4, 8, 12, and 18, 24 months after C1D1, and yearly after) will be required for banking at the University of Chicago for later M-spike analysis with a new elotuzumab interference assay. This assay will use mass spectrometry and is not commercially available. This assay is proprietary to BMS, which will receive banked samples and perform this assay. Assay results will not be used for clinical decision-making, but rather to assess and confirm the primary endpoint of stringent CR.

Additionally, for subjects who have a plasmacytoma or disease measured by imaging at baseline, plasmacytoma evaluations and radiographic imaging should be completed as per standard of care and in accordance with IMWG response criteria for multiple myeloma. Subjects who achieve SD, PR, or CR will continue therapy until disease progression. Subjects with disease progression will discontinue the treatment regimen and be removed from protocol.

2. OBJECTIVES

2.1. Primary Objective

• The primary efficacy endpoint will be the rate of sCR and/or the rate of negative MRD by next generation gene sequencing (NGS) by clonoSEQ (Adaptive Biotechnologies) at the end of 8 cycles among non-transplant candidates and transplant candidates who agreed to defer transplant

2.2. Secondary Objectives

- To evaluate the safety and tolerability of elotuzumab in combination with KRd, when administered to subjects with newly diagnosed multiple myeloma.
- Determine the rate of MRD by next generation gene sequencing (NGS) by clonoSEQ (Adaptive Biotechnologies) and by multi-color flow cytometry (MFC) at the end of Cycle 4, 8, and 12 for all subjects, and end of C18 (for subjects who are MRD+ at the end of C8 but MRD- at the end of C12 only), 24 months after C1D1, and yearly after that.
- Estimate time to event, including duration of response (DOR), progression-free survival (PFS), time to progression (TTP), and overall survival (OS).

2.3. Exploratory Objectives

- GEP, proteomics, and gene sequencing to evaluate the correlation between treatment outcome and pre-treatment subject profile.
- Immunologic correlative studies including FcγRIIIa V genotype.

3. STUDY ENDPOINTS

3.1. Primary Endpoints

To determine the rate of sCR and/or the rate of negative MRD by NGS at the end of 8 cycles per IMWG criteria.

3.2. Secondary Endpoints

- Evaluate the safety and tolerability of elotuzumab in combination with KRd by monitoring AE rate, classification, and relation to study drug
- Compare rates of MRD between MFC and NGS at the end of cycles 4, 8, and 12 for all subjects, and end of C18 (for subjects who are MRD+ at the end of C8 but MRD- at the end of C12 only), 24 months after C1D1, and yearly after that.
- Estimate the time to event including duration of response (DOR), progression-free survival (PFS), time to progression (TTP), and overall survival (OS)

3.3. Tertiary/Exploratory Endpoints

- Conduct GEP, Proteomic, and gene sequencing studies to evaluate the correlation between treatment outcome and pre-treatment subject profile
- Conduct immunologic correlative studies including FcyRIIIa V genotype

4. INVESTIGATIONAL PLAN

4.1. Overview of Study Design and Dosing Regimen

This is a Phase 2, open-label, multicenter study studying the safety and tolerability to the combination therapy of elotuzumab, lenalidomide, carfilzomib, and dexamethasone for newly diagnosed subjects with multiple myeloma requiring systemic chemotherapy.

Subjects will receive treatment until disease progression or unacceptable toxicity (whichever occurs first). The primary endpoint of this Phase 2 study is to determine the rate of sCR and/or the rate of negative MRD by NGS at the end of 8 cycles per IMWG criteria and to evaluate the safety and tolerability of elotuzumab in combination with KRd, when administered to subjects with newly diagnosed multiple myeloma.

4.2. Study Procedures

On cycles 1 and 2, subjects will receive elotuzumab weekly on days 1, 8, 15, and 22 of a 28-day cycle at 10mg/kg. From cycle 3 onward, elotuzumab will be dosed every other week on days 1 and 15 at 10mg/kg.

Carfilzomib will be dose escalated on cycle 1 as follows: 20 mg/m^2 on day 1, 56mg/m^2 on day 8, and 56mg/m^2 on day 15. Between cycles 2-8, carfilzomib will be given on days 1, 8, and 15 of a 28-day cycle at 70 mg/m². From cycle 9 onward, carfilzomib will be given at the best-tolerated dose on days 1 and 15 of a 28-day cycle. Splitting carfilzomib dose to 27 mg/m^2 on days 8, 9 and 36 mg/m^2 on days 15, 16, and in subsequent cycles on days 1, 2, 8, 9, 15, 16 - as in the original KRd 2-day weekly schedule – will be allowed based on discussion with the lead PI.

Lenalidomide will be given initially at 25mg per dose daily on days 1-21 of a 28-day cycle for cycles 1-8. From cycle 9 onward, lenalidomide will be dosed at last tolerated dose daily on days 1-21 of a 28-day cycle.

Dexamethasone will initially be give 40 mg weekly (cycles 1-4), which in the first cycle will be split into two doses as follows: 20mg of dexamethasone will be given IV on days 1, 8, and 15 no more than 3 hours prior to elotuzumab infusion and 20mg on days 2, 9, and 16 will be taken PO. If in the course of dose modification carfilzomib is split, dex will be given prior to carfilzomib. However, most pts will not be given carfilzomib on days 2, 9, and 16. On Day 22 of cycle 1,

40mg dexamethasone will be given IV no longer than 3 hours prior to elotuzumab. In cycles 2-4 40mg dexamethasone will be taken PO (or IV) on days 1, 8, 15, and 22. On days when dexamethasone coincides with elotuzumab, dexamethasone will be taken no longer than 3 hours prior to elotuzumab infusion. For cycles 5+ dexamethasone will be reduced to 20 mg PO or IV weekly.

Dose modifications will be mandated based on aggressive schedule of dose modification for toxicities as per specific guidelines. Otherwise, subjects will continue at their best tolerated dose of lenalidomide on days 1-21 and their best tolerated dose of carfilzomib on days 1, 8, 15 in cycles 1-8 and days 1, 15, in cycles 9-12 (in subjects with MRD- disease at the end of cycle 8 and 12) or cycles 9-18 (in subjects with MRD+ disease at the end of cycle 8 but MRD- at the end of cycle 12) or cycles 9-24 (in subjects with MRD+ disease at the end of cycle 8 and 12). See section 1.7.

All subjects will have weekly visits for toxicity assessments in the first cycle and then monthly from cycles 2+. Disease assessments will start on Cycle 1 Day 15 and then will be done on clinic visits on day 1 of each cycle. Treatment will continue on protocol for up to 24 months or if elotuzumab, carfilzomib and lenalidomide are permanently discontinued. Toxicity will be graded using the National Cancer Institute Common Terminology Criteria for Adverse Events version 4. Subject who complete 12 cycles (who are MRD-negative at the end of cycle 8 and 12), 18 cycles (who were MRD-positive at the end of cycle 8 but MRD-negative at the end of cycle 12), or 24 cycles (who were MRD-positive after cycle 8 and 12) of E-KRd, will then continue elotuzumab, lenalidomide, dexamethasone (E-Rd) maintenance. This regimen will continue until there is progression of the disease or the toxicities require discontinuation of the drug.

Minimal residual disease analysis will be performed at the end of cycle 8 and 12 to determine the course of treatment (either move to ERd maintenance at the end of 12, 18, or 24 cycles of E-KRd. See section 1.7). MRD analysis will be performed using the most recent Spanish protocol by multiparameter flow cytometry (10-color) and by Next Generation Sequencing (NGS). MRD will be assessed in all bone marrow samples at the beginning of the study, after cycles 4, 8, 12, and 18 (when applicable), 24 months after C1D1, yearly after that, and at any time a bone marrow biopsy is completed to assess response for suspected nCR (or VGPR when nCR assessment is not possible). From the time nCR (or VGPR) is established, MRD analysis should continue at 12-month intervals from randomization up to 6 years in subjects with ongoing sCR. If a confirmatory BM for nCR is scheduled within 2 months of a hallmark BM, it is acceptable to wait until the hallmark timepoint. All flow cytometry analysis will be performed at the University of Chicago, based on a consensus for the most recent technical guidelines and flow cytometry (current EuroFlow technique) parameters as outlined by Orfeo et al. (MRD IMWG meeting New York, NY 2014). The same samples will be evaluated by Adaptive Biotechnologies using clonoSEQ® platform after processing at the University of Chicago site. For this purpose, sites will be required to provide a fresh screening BM sample at all timepoints. At screening only, alternatively, non-decalcified slides from the BM aspirate, or FFPE clot slides can be used to establish a baseline for MRD samples analyzed by Adaptive Biotechnologies. Decisions to change treatment at indicated time points will be based primarily on MRD results by NGS. Only if NGS testing is not successful (i.e. either at the calibration or measurement step), flow-based results will be used for decision about duration of E-KRd treatment.

Treatment responses will be assessed by serum and urine monoclonal protein electrophoresis and immunofixation and serum free light chains (SFLC) and where needed by serum protein immonglobulins at Cycle 1 Day 15, then at Cycle 2 Day 1 and then at the beginning of each subsequent cycle. A serum sample from blood at landmark timepoints (after C4, 8, 12, and 18, 24 months after C1D1, and yearly after) will be required for banking at the University of Chicago for later M-spike analysis with a new elotuzumab interference assay. The analysis of banked samples by elotuzumab interference assay will be performed using Mass Spectrometry by BMS

Subjects with stable disease or better will continue treatment until disease progression or the development of unacceptable toxicities. All subjects will then undergo a final visit (end of treatment visit) within 30 (+/-7) days of last dose of study medication.

4.2.1.MRD Detection Methods

The tests used Minimal Residual Disease (MRD) after cycles 8 and 12 is considered experimental and has not been approved by the US Food & Drug Administration (FDA) for use in evaluating MRD disease in multiple myeloma.

The flow cytometry analysis procedure used to determine MRD is performed on a NAVIOS FLOW CYTOMETER SYSTEM manufactured by BECKMAN COULTER, INC., using a laboratory developed assay. The Premarket Notification 510(k) (Number K130373) for the device can be found using the following link.

https://www.accessdata.fda.gov/scripts/cdrh/cfdocs/cfpmn/pmn.cfm?ID=K130373.

4.2.2. Number of Centers

A total of 5 centers in the US will participate.

4.2.3. Definition of Treatment Cycle and Duration

Each treatment cycle is 28 days. The study is planned to start in Q4 2016 with respect to first subject in (FSI). With an expected accrual rate of 2-4 subjects per month across 5 centers, and a total number of 40-55 subjects planned, the anticipated enrolment period is 12 -18 months. Hence the last subject in will be included not prior to Q4 2017. The length of treatment period will be up to 24 months. Subjects will be followed for survival for up to 6 years since their enrollment or until death, whichever occurs first.

4.2.4. Treatment Phase

Treatment will be continued until progression of disease according to IMWG criteria, until the subject goes into transplant, unacceptable toxicities occur in individual subjects, or consent is withdrawn.

4.2.5.End of Treatment Visit

Subjects that discontinue from treatment will undergo an end of treatment visit, regardless of the reason of discontinuation, 30 (+/-7) days after the last dose of study medication.

4.2.6.Long Term Follow Up

Subjects will be followed up every 3 months for progression and survival after the end of treatment. Subjects will be followed for survival for up to 6 years after enrollment or until death, whichever occurs first. The follow up will be done over the phone.

5. SUBJECT SELECTION

5.1. Inclusion Criteria

Subjects must meet all of the following inclusion criteria to be eligible to enroll in this study. No enrollment waivers will be granted.

1. Newly diagnosed, previously untreated myeloma requiring systemic chemotherapy

- a. Prior treatment of hypercalcemia or spinal cord compression or active and/or aggressively progressing myeloma with corticosteroids and/or lenalidomide and/or bortezomib/PI-based regimens does not disqualify the subject. The corticosteroid treatment dose should not exceed the equivalent of 160 mg of dexamethasone in a 4 week period or not more than 1 cycle of lenalidomide and/or PI-based therapy. A higher total dose of corticosteroid is allowed for the management of cord compression at the discretion of the PI, as long as the subject does not exhibit any steroid related toxicities at the initiation of study treatment.
- 2. Both transplant and non-transplant candidates are eligible.
- 3. Diagnosis of symptomatic multiple myeloma as per current IMWG uniform criteria prior to initial treatment
- 4. Monoclonal plasma cells in the BM 10% or presence of a biopsy-proven plasmacytoma
- 5. Measurable disease, prior to initial treatment as indicated by one or more of the following:
 - a. Serum M-protein ≥ 1 g/dL
 - b. Urine M-protein $\geq 200 \text{ mg/}24 \text{ hours}$
 - c. If serum protein electrophoresis is felt to be unreliable for routine M-protein measurement, then quantitative immunoglobulin levels are acceptable ($\geq 1~g/dL$)
 - d. Involved serum free light chains ≥ 10 mg/dL provided that free light chain ratio is abnormal
- 6. Screening laboratory values must meet the following criteria and should be obtained within 21 days prior to enrollment

i. WBC $\geq 2000/\mu L$

ii. Platelets $\geq 75 \times 10^3/\mu L$

iii. ANC >1000/μL

iv. Hemoglobin > 8.0 g/dL

- v. Serum creatinine ≤ 1.5 x ULN or creatinine clearance (CrCl) ≥ 50 mL/min
 - a) Use the Cockcroft-Gault formula below):
 - o Female CrCl = (140 age in years) x weight in kg x 0.85
 - 72 x serum creatinine in mg/dL
 - o Male CrCl = (140 age in years) x weight in kg x 1.00
 - 1. 72 x serum creatinine in mg/dL

- b) Alternatively to Cockroft-Gault formula of CrCl, 24hr urine CrCl can be used
- vi. $AST/ALT \leq 3 \times ULN$
- vii. Total Bilirubin ≤ 1.5 x ULN (except subjects with Gilbert Syndrome, who can have total bilirubin < 3.0 mg/dL) or ≤ 2 x ULN if lenalidomide is being prescribed.
- 7. Males and females \geq 18 years of age
- 8. ECOG performance status of 0-1
- 9. Females of childbearing potential (FCBP) must have 2 negative pregnancy tests (sensitivity of at least 25 mIU/mL) prior to initiating lenalidomide. The first pregnancy test must be performed within 10-14 days before and the second pregnancy test must be performed within 24 hours before lenalidomide is prescribed for Cycle 1 (prescriptions must be filled within 7 days).
- 10. FCBP must agree to use 2 reliable forms of contraception simultaneously or to practice complete abstinence from heterosexual intercourse during the following time periods related to this study: 1) for at least 28 days before starting lenalidomide; 2) while participating in the study; and 3) for at least 28 days after discontinuation from the study.
- 11. Male subjects must agree to use a latex condom during sexual contact with females of childbearing potential while participating in the study and for at least 28 days following discontinuation from the study even if he has undergone a successful vasectomy.
- 12. All study participants in the US must be consented to and registered into the mandatory Revlimid REMS® program and be willing and able to comply with the requirements of Revlimid REMS®.
- 13. Voluntary written informed consent

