Study Design	This study will be a multi-center, open-label, Phase 2 study. Those newly diagnosed with MM requiring systemic chemotherapy will be eligible for enrollment. Dose Schedule and Dose Levels in 28-day cycles		
	Subjects will be tested for Minimal Residual Disease (MRD) by Next Generation Sequencing (NGS) and flow cytometry after cycles 8 and 12. A treatment decision will be made after cycle 12 based on these results. There are three possible outcomes based on the IFM trial (Avet-Loiseau et al., 2015): 1) if the subject is MRD-negative by NGS after cycle 8 and 12, the subject will be go on E-Rd maintenance until disease progression. 2) If the subject is MRD-positive after cycle 8 but MRD-negative after cycle 12, 6 more cycles of E-KRd will be given and at the end of 18		

cycles, the subject will go on E-Rd maintenance until disease progression. 3) Finally, if the subject is MRD-positive at both instances, 12 additional cycles of E-KRd will be given and at the end of 24 cycles total, the subject will go on E-Rd maintenance until disease progression. For subjects for whom NGS evaluation is not successful because of inadequate calibration specimen or not-evaluable follow-up specimen, the results of MRD testing by flow will be used for treatment decisions.

Elotuzumab

Cycle 1-2 Days 1, 8, 15, 22	Cycle 3+ Days 1 and 15
10 mg/kg IV infusion weekly	10 mg/kg IV infusion every 2
starting Cycle 1 day 1	weeks starting Cycle 3 day 1

^{*} On days when elotuzumab and carfilzomib coincide, carfilzomib will be infused first followed by elotuzumab infusion

Carfilzomib

Cycle 1*	Cycle 2-8	Cycle 9+
IV infusion Day 1: 20 mg/m ² Day 8 & 15: 56 mg/m ²	IV infusion 70 mg/m ² : Days 1, 8, and 15	IV infusion Last tolerated dose on Days 1 and 15

^{*}Dose escalation may need to be modified based on toxicities in the prior week. Please see dose modifications section.

Lenalidomide

Cycle 1-8	Cycle 9+
PO at 25 mg per dose on Days 1-	PO at last tolerated dose for days
21	1-21

Dexamethasone

Cycle 1-2

Tx Days 1, 8, 15	Tx Days 2, 9, 16	Tx Day 22
20 mg IV no more than 3 hrs prior to elotuzumab infusion	20 mg PO the day after elotuzumab infusion	40mg IV (C1 only) or PO, no more than 3 hrs prior to elotuzumab infusion

Cycle 3-4

Tx Days 1, 8, 15, 22

40mg PO weekly. On days when dexamethasone and elotuzumab coincide, dexamethasone should be taken no more than 3 hours prior to elotuzumab infusion

Cycle 5+

Tx Days 1, 8, 15, 22

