6.1. Treatment Regimen

Please refer to the Study Calendar (Appendix 6 for an overview).

After screening, eligibility determination and enrollment, subjects will receive elotuzumab, carfilzomib, lenalidomide, and dexamethasone, in 28 day cycles until progression, unacceptable toxicity or subject withdraws consent.

A subject is considered to be off-treatment following a 30-day safety follow-up period after the last treatment. Long-term follow-up for survival will be 6 years total from the time of enrollment.

Cycles 1 - 2

Agent	Premedication and Precautions	Schedule	Dose	Route
Elotuzumab	Please refer to Section 6.3	Days 1, 8, 15, 22	10 mg/kg	Intravenous-See appendix B for more details
Carfilzomib	Please refer to Section 6.3			
Lenalidomide	None	Days 1-21 of each cycle	25 mg	Oral
	Take with food;	Days 1, 8, 15	20 mg	IV
Dexamethasone recommended to be taken in the morning	recommended to be taken	Days 2,9, 16	20 mg	Oral
	Day 22	40 mg	Oral	

Cycles 3 - 4

Agent	Premedication and Precautions	Schedule	Dose	Route
Elotuzumab	Please refer to Section 6.3	Days 1 and 15	10 mg/kg	Intravenous-See appendix B for more details
Carfilzomib	Please refer to Section 6.3			
Lenalidomide	None	Days 1-21 ofeach cycle	25 mg	Oral
Dexamethasone	Take with food;recommende d to be taken in the morning	Days 1, 8,15, 22	40 mg	Oral

Cycles 5+

Agent	Premedicationand Precautions	Schedule	Dose	Route
Dexamethasone	Takewithfood; recommended to be taken in the morning	Days1, 8,15,22	20 mg	Oral

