6.4.3. Lenalidomide Administration

Lenalidomide will be provided in accordance with the Revlimid REMS® program of Celgene Corporation. Per standard Revlimid REMS® requirements, all physicians who prescribe lenalidomide for research subjects enrolled into this trial must be registered and must comply with all requirements of the Revlimid REMS® program. Prescriptions must be filled within 7 days.

Subjects will receive lenalidomide as follows in 28-day cycles:

- Cycle 1-8: 25 mg days 1-21
- Cycles 9+: best tolerated dose days 1-21

Lenalidomide should be taken each evening at approximately the same time. Lenalidomide is taken with water on a full or empty stomach. Subjects should not break, chew or open capsules. Late doses of Lenalidomide should if possible be taken on the assigned day but should not be made up the next day. Vomited doses will not be made up. Subjects should be instructed to never take Lenalidomide past Day 21 of each cycle.

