6.6. Dose-Modification Guidelines

The following sections and tables summarize dosing modifications of elotuzumab, carfilzomib, lenalidomide, and dexamethasone to manage possible toxicity. Dose modifications different from those stated in the protocol should be discussed with the Lead Principal Investigator. Administration of carfilzomib and lenalidomide will be discontinued in the event of any other toxicity that, in the opinion of the Lead, Secondary Site, or Treating Investigator, warrants discontinuation.

In addition to dose reductions, administration of elotuzumab, carfilzomib and lenalidomide will be held temporarily in the event of a treatment-related toxicity at the Treating Investigator's discretion. Study treatment may be reintroduced if resolution of the event to the baseline value or to \leq Grade 1 within 21 days; otherwise study drug will be permanently discontinued. Any deviations from this plan must be approved by the Lead Principal Investigator.

If a subject's elotuzumab administration is delayed on day 1 of a cycle, carfilzomib, lenalidomide, and dexamethasone will also be delayed until the elotuzumab is resumed, which would then become the new day 1 of that cycle.

If a subject's elotuzumab is held in the middle of a cycle, carfilzomib, dexamethasone, and lenalidomide dosing will continue as scheduled. If the subject's elotuzumab is delayed during the cycle and is resumed within the designated window, (+/-3 days Cycles 1 and 2; +/-7 days Cycles 3 and beyond) the subject may receive the scheduled dose. If the elotuzumab is not resumed within the given window (+/-3 days Cycles 1 and 2; +/-7 days Cycles 3 and beyond), the subject is to omit that dose, and resume dosing at the next dosing time point.

If a study drug (except dexamethasone) is discontinued, the subject may continue on trial. However, if the discontinuation happens prior to the end of cycle 8 (1^{ary} endpoint), the subjects will Page 45

continue to be treated and will only be included on the intent to treat analysis.

All clinically-significant non-hematologic toxicities must be resolved to Grade 1 or baseline.

Dose reduction levels of elotuzumab, carfilzomib, lenalidomide, and dexamethasone for toxicity management of individual subjects are provided below:

Table 6-1 Carfilzomib Dose Adjustments

Nominal carfilzomib dose	Dose -1	Dose -2	Dose -3	Dose -4
70 mg/m^2	56 mg/m^2	45 mg/m^2	36 mg/m^2	27 mg/m^2

Table 6-1 Lenalidomide Dose Adjustments

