Tumor lysis syndrome (≥ 3 of the following: ≥ 50% increase in creatinine, uric acid, or phosphate;≥ 30% increase in potassium;≥ 20% decrease in calcium; or ≥ 2-fold increase in LDH	Hold lenalidomide until all abnormalities in serum chemistries have resolved. Reinstitute at full doses.	Hold carfilzomib until all abnormalities in serum chemistries have resolved. Reinstitute at full doses.	Hold Upon resolution elotuzumab can be restarted at the treating physician's discretion		
Infection Grade 3 or 4	Hold lenalidomide until systemic treatment for infection is completed. If no neutropenia, restart lenalidomide at full dose. If neutropenic, follow neutropenic instructions.	Hold carfilzomib until systemic treatment for infection is completed If no neutropenia, restart carfilzomib at full dose. If neutropenic, follow neutropenic instructions.	Hold Upon resolution elotuzumab can be restarted at the treating physician's discretion		
Herpes zoster or simplex of any grade	Hold lenalidomide until lesions are dry. Reinstitute at full doses.	Hold carfilzomib until lesions are dry. Reinstitute at full doses.	Hold When lesions are dry elotuzumab can be restarted at the treating physician's discretion		
Grade 2 neuropathy with pain or any Grade 3 neuropathy	Hold until ≤ Grade 2. Then restart lenalidomide at 1 dose decrement	Withhold until toxicity is resolved or returned to baseline After resolution, consider if restarting CFZ at the same dose or at a reduced dose is appropriate. If tolerated, the reduced dose may be escalated to the previous dose at the discretion of the physician	Hold Upon resolution elotuzumab can be restarted at the treating physician's discretion		
Grade 4 neuropathy	Discontinue	Discontinue	Hold Upon resolution elotuzumab can be restarted at the treating physician's discretion		
Renal dysfunction					
Serum creatinine > 2 mg/dL	Base dose reduction on calculated GFR (below)	Base dose reduction on calculated GFR (below)	Hold Upon resolution elotuzumab can be		

Table 6-6 Dose Modifications for Non-hematologic Toxicity

	Recomme	nded Action	
Non-heme toxicity	Lenalidomide	Carfilzomib	Elotuzumab
			restarted at the treating physician's discretion
CrCl>60 mL/min	Full dose	Full dose	Full dose
CrCl <60 mL/min > 30 mL/min	Reduce lenalidomide to 10 mg every 24 h; may reinstate prior dose if, after 2 cycles, CrCl normalizes	Full dose	Full dose

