- 20. Carfilzomib days 1, 8, and 15 of cycles 1-8 and 1 and 15 of cycles 9+ at assigned dose. Cycle 1 step-up dosing is required: 20mg/m² Day 1; 56mg/m² Day 8; 56mg/m² Day 15. On Cycle 2 day 1, the dose of carfilzomib will be escalated to 70mg/m² and will continue to be dosed at this level. Hydration directions from section 6.3.2 must be followed
- 21. Lenalidomide must be prescribed through and in compliance with the RevlimidREMS™ program of Celgene Corporation. Prescriptions must be filled within 7 days. Consideration should be given to prescribing lenalidomide 5 to 7 days in advance of Day 1 of each cycle to allow time for required subject and prescriber surveys, and drug shipment to subject.

- 22. Lenalidomide dosing Days 1-21. Cycles 1-8 Lenalidomide will be administered at 25 mg. From cycle 9+ Lenalidomide will be administered at best tolerated dose on days 1-21 of a 28-day cycle. Lenalidomide should be taken in the evening at approximately the same time each day.
- 23. On cycles 1-2, dexamethasone will be split into two doses as follows: 20mg of dexamethasone will be given IV on days 1, 8, and 15 no more than 3 hours prior to elotuzumab infusion and between 30min and 4 hours prior to carfilzomib, and 20mg will be taken PO on days 2, 9, and 16. On Day 22 of cycle 1, 40mg dexamethasone will be taken PO no longer than 3 hours prior to elotuzumab. When dexamethasone, carfilzomib and elotuzumab coincide, dexamethasone will be dosed first, followed by carfilzomib infusion, and finally elotuzumab will be infused.

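### Eligibility admits creatinine clearance below 60 mL/min, but lenalidomide starts at 25 mg for all, and the plan does not say whether its own renal dose rows apply on Cycle 1 Day 1

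*Combined protocol and SAP*

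**What the plan says.** **Eligibility.** Section 5.1, criterion 6 v, and the matching synopsis item accept "Serum creatinine ≤ 1.5 x ULN or creatinine clearance (CrCl) ≥ 50 mL/min". Clearance is by Cockcroft-Gault, with a 24-hour urine measurement as the alternative.

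**Starting dose.** Section 4.2: "Lenalidomide will be given initially at 25mg per dose daily on days 1-21 of a 28-day cycle for cycles 1-8". Section 6.4.3: "Cycle 1-8: 25 mg days 1-21". Appendix 6, note 22: "Cycles 1-8 Lenalidomide will be administered at 25 mg". The synopsis and the Cycles 1-2 and 3-4 tables in 6.1 also give 25 mg (in 6.1 the schedule cell reads "Days 1-21 of each cycle"). None of these attaches a renal condition.

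**Renal dosing.** Section 6.6 opens: "The following sections and tables summarize dosing modifications of elotuzumab, carfilzomib, lenalidomide, and dexamethasone to manage possible toxicity". The renal block of Table 6-6 (6.6.1.2) starts with a row for serum creatinine above 2 mg/dL, whose lenalidomide and carfilzomib entries read "Base dose reduction on calculated GFR (below)". The rows beneath give lenalidomide at full dose above 60 mL/min, 10 mg every 24 h between 30 and 60 (the previous dose may return if clearance normalizes after 2 cycles), and 15 mg every 48 h below 30. A separate row covers dialysis.

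**Pointers.** For renal dose reduction, the carfilzomib text in 6.4.2 cites Table 6-1 and that in 6.10.4 cites Table 6-7.

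**The concern.** The eligibility rule admits a range of clearance in which the plan's own table does not give 25 mg, and no sentence connects the two on Cycle 1 Day 1. If Table 6-6 is used only for changes on treatment, a clearance of 55 mL/min gets 25 mg when present at entry and may get 10 mg when reached later.

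Patient safety is at stake: higher lenalidomide exposure than the plan's table sets for that clearance, in Cycles 1-8 of a four-drug regimen. Consistency is also at stake, because sites that resolve the gap differently will start similar subjects on different doses.

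Other provisions do not close the gap. Section 6.5 asks only that creatinine return to baseline before carfilzomib in Cycles 1 and 2, which a low baseline clearance already meets. Central approval under 5.3.1 confirms eligibility, and these subjects are eligible. Section 6.10.3 itself names clearance below 50 mL/min as a risk group for tumor lysis, so such subjects are foreseen.

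**Working it through.** The plan gives no figure for this point, so the check sets its rules side by side and applies its printed formula.

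**1. Who can enter.** From 5.1: CrCl = (140 - age) x weight (x 0.85 if female) / (72 x creatinine). Ages, weights and a creatinine upper limit of normal (ULN) of 1.0-1.2 mg/dL are my assumptions; the documents give none of them.

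| Subject | Calculation | CrCl, mL/min | Entry route |
|---|---|---|---|
| A: man, 70 y, 70 kg, creatinine 1.2 | 4900 / (72 x 1.2) | 56.7 | either limb |
| B: woman, 70 y, 60 kg, creatinine 1.0 | 3570 / (72 x 1.0) | 49.6 | creatinine limb only |
| B at creatinine 1.5 | 3570 / (72 x 1.5) | 33.1 | creatinine limb only |
| C: man, 50 y, 90 kg, creatinine 2.1 | 8100 / (72 x 2.1) | 53.6 | CrCl limb only |

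Man A falls below 60 once creatinine exceeds 4900 / (72 x 60) = 1.13 mg/dL. Woman B does so above 3570 / (72 x 60) = 0.83 mg/dL, and reaches 30 only at 3570 / (72 x 30) = 1.65 mg/dL. The main case is therefore clearance 30-60.

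**2. Dose per 21-day course.**
- As the dosing sections state: 25 x 21 = 525 mg.
- Table 6-6 row for 30-60: 10 x 21 = 210 mg; 525 / 210 = 2.5.
- Table 6-6 row below 30: 15 mg on days 1, 3, ..., 21 = 11 x 15 = 165 mg; 525 / 165 = 3.2.

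**3. Does the table reach these subjects?** This depends on the creatinine row that heads the renal block.
- If the clearance rows stand alone, the row for A, B and C is 10 mg.
- If they apply only above 2 mg/dL, A and B never reach the 10 mg row and would stay on 25 mg on study too. Only C conflicts with the table. The creatinine limb cannot admit anyone above 2 mg/dL unless the ULN exceeds 2 / 1.5 = 1.33 mg/dL, so under the assumed ULN the conflict is then confined to the CrCl limb.
- The elotuzumab column points against nesting, because the creatinine row holds elotuzumab while every clearance row gives it at full dose. That is not conclusive.

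**4. Do the pointers settle it?** No. Two tables are numbered 6-1, for carfilzomib and lenalidomide; both list dose levels only. No Table 6-7 appears. Section 6.9 also cites 6-7, for heart failure, which Table 6-6 covers, so 6-7 looks like an old number for 6-6.

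**The case against.** The strongest reply is that Table 6-6 already supplies the rule. Its rows use absolute clearance, not a fall from baseline. Section 6.10.4 stresses knowing renal function when dosing, creatinine must be reviewed before each carfilzomib dose in Cycles 1 and 2, and 6.6 treats 25 mg as a nominal dose. A site could reasonably start a subject with clearance 55 mL/min at 10 mg. This stands as a possible interpretation. Against it, section 6.6 ties the tables to toxicity, the row speaks of reducing and of returning to a previous dose, and a subject entering at 55 has no previous dose.

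The creatinine row is a second fair objection, and it limits what can be said about A and B. It does not supply a starting rule.

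Third, Appendix 5 links to the lenalidomide prescribing information. Its content is not in the documents, and no dosing section tells sites to take the starting dose from it. It may help an individual prescriber but does not settle the protocol rule.

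Fourth, both faulty pointers concern carfilzomib, which stays at full dose at 30-60. They are clerical and secondary, though they sit in operative dosing text.

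A reader might infer that the plan orders an overdose, or gives two contradictory Day 1 instructions. The documents do not support that: the only explicit Day 1 instruction is 25 mg, and whether the table overrides it is left open.

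**Conclusion.** The point holds as an unresolved conflict between the stated starting dose and the plan's own renal table. Criterion 6 v admits clearance below 60 mL/min, all the dosing sections give 25 mg unconditionally, and the text does not say whether Table 6-6 governs entry. Taken literally, the dose at clearance 30-60 is 2.5 times the row for that clearance.

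The size rests on reading the clearance rows as independent of the creatinine trigger; otherwise the conflict narrows to subjects such as C. The number affected cannot be estimated, and the examples rest on assumed ages, weights and ULN.

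A reader might also infer a general problem with starting carfilzomib below 30 mL/min. Entry at that level needs an older or smaller subject with raised creatinine, and performance status 0-1 and the geriatric-score exclusion may make it rarer still. It is not part of this conclusion. Confidence is moderate; the change should be made.

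**What to change.** State in 6.4.3 that the Cycle 1 Day 1 lenalidomide dose follows screening clearance (Cockcroft-Gault or 24-hour urine), whatever the serum creatinine:
- 60 mL/min or above: 25 mg;
- 30 to below 60: 10 mg daily;
- below 30: 15 mg every 48 h.

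Allow a rise to 25 mg if clearance normalizes after 2 cycles, since a subject started low has no earlier dose to return to. These cut-offs also assign values of exactly 30 and 60, which the table leaves uncovered. Cross-refer to the rule in the synopsis, 4.2, both 6.1 tables and Appendix 6 note 22. Change the renal references in 6.4.2 and 6.10.4 to Table 6-6.

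Eligibility need not change. A Day 1 carfilzomib hold below 30 is deliberately left out: its interaction with the one-decrement restart (6.5) and the 21-day limits (6.5, 6.6) would need its own decision.

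**Cost.** A short paragraph, cross-references and two table numbers. There is no new test, because age, weight and creatinine are already collected. The real downside is exposure. At clearance 30-60, the Cycles 1-8 total falls from 8 x 525 = 4200 mg to 2 x 210 + 6 x 525 = 3570 mg (85%) if raised after 2 cycles, or to 8 x 210 = 1680 mg (40%) if never raised. This may affect comparison with the historical 30% rate in 10.2.1, whose renal dosing is not given.

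For scale, the 10.2.1 rule of 17 or more responders in 40 has exact power 86.6% at a true rate of 50%, matching the stated figure of a little over 85%. The shares and response losses below are assumptions:
- 10% affected, 5-point loss: 50 - 0.10 x 5 = 49.5%, power 85.2%;
- 10% affected, 10-point loss: 49%, power 83.7%;
- 30% affected, 10-point loss: 50 - 0.30 x 10 = 47%, power 76.6%.
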